Study Population. Our clinical population will be men and women (N=5 to 7) 21-60 years old who are currently living with HIV (under antiretroviral therapy for 5+ years with a suppressed viral load).

Recruitment strategy. Co-I [name] has extensive experience in HIV patient recruitment and will oversee the recruitment team, during the recruitment phase, as well as the safety monitoring. Five PLWH (men and women) will be primarily recruited from The SHARC Registry (IRB# 201400073), a UF-IRB-approved registry of over 600 HIV patients who have agreed to be contacted about future research. Written informed consent will be obtained, and blood will be collected at the UF CTRB clinical research center. Inclusion criteria are: ability to read English and provide written consent; willingness to take CBD and to participate in follow up for two months; older than 21 and younger than 60; under antiretroviral therapy for 5+ years and suppressed viral load (CD4 count <350cells/ml); patients must agree to practice acceptable methods of birth control, namely sterilization (female tubal ligation or occlusion, male vasectomy), long-acting reversible contraceptives (intrauterine devices, hormonal implants), short-acting hormonal methods (pill, mini pills, patch, shot, vaginal ring), and condoms.

The main exclusion criterion will be conditions/medications that may impair the immune response (e.g. rheumatoid arthritis, cancer, diabetes chronic infections, CAD, cellulitis, autoimmune diseases such as lupus, sarcoidosis, and all medications they may affect inflammation such as aspirin, steroids, statins);), pregnancy, and current marijuana or CBD use (urine drug screen). Further exclusion criteria will be: excluding subjects taking anti-seizure medicines, with any history of seizure disorder or head trauma, any history of hepatic/liver disease or renal disease, any history of cardiovascular diseases; women who are lactating (in addition to existing exclusion criteria for pregnancy). Co-I [name] (a physician) will review conditions/medications after the initial interview before the patient is enrolled to exclude risks of drug interactions or hepatotoxicity. UF/Shands staff and students will not be considered for enrollment. Presence of chronic pain will not be considered as a necessary condition for enrollment.

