Each participant will be provided two 30mL bottles (2000mg CBD per bottle) with a syringe dropper during their initial (baseline) visit with instructions/demonstration to administer the solution under the tongue (0.5 cc ~1/2 dropper) twice per day (BID) 8-12 hours apart (morning and evening) at the prescribed daily dosage (63mg/day). The sublingual route of administration allows the product to be absorbed directly into venous circulation, and thus bypasses the liver and eliminates the consequences of first pass metabolism; ultimately increasing its bio-availability. The bioavailability of CBD administered orally (including sublingual) is estimated to be 13-19% and its half-life estimated to be around 18-32 hours.

Physical Discomforts and Intervention Risks:

In previous clinical trials using hemp-derived products administered orally (liquid or capsule) and swallowed, a small percentage of patients experienced tiredness, change in appetite and gastro-intestinal discomfort following ingestion. We will be using daily doses of hemp extract that are considerably lower than the daily doses used in the clinical trials. Therefore, the chance of our participants experiencing these side effects is minimal.

Occasionally one or more of the following potential side effects of taking blood samples may occur: pain, bruising, slight bleeding, light-headedness, fainting and (rarely) an infection. A trained technician will be drawing the blood.

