Safety Monitoring and Stopping Criteria: Safety monitoring will occur during the initial baseline visit as well as throughout the participant's duration in the study, including a 1week follow-up contact after study termination. As noted below, the baseline assessment conducted during the first visit will include a brief physical exam (including vital signs) and a thorough medical and psychiatric history, including a review of past medical history, concomitant medications, inclusion/exclusion criteria, and potential contraindications. Safety monitoring will include active and passive surveillance procedures using preexisting safety monitoring guidelines. Participants will be assessed actively at each laboratory visit by study personnel using the side effects/adverse events checklist. Each participant will be read each side effect/adverse event from the checklist and instructed to self-report as yes (go) or no (no go). If a participant experiences any of the side effects/adverse events from the checklist provided at the baseline visit, study personnel will then contact the study physician ([name]) for consultation. The side effects/adverse events will be triaged as mild, moderate or severe, and a determination will be made by the study physician as to whether the side effect/adverse event is due to the investigational test article or some other circumstance (e.g. food poisoning). If the reaction or event is determined to be due to the investigational test article and graded moderate to severe by the study physician, the participant will then be instructed to stop participation and advised to seek medical care by their primary physician or hospital. (Refer to stopping

criteria below). Any serious adverse reaction or event will be followed until full resolution. All adverse reactions and events will be reported to the UF IRB within 24-48-hrs and documented in the participant's file (redcap). The PI/physician decides that the participant should be withdrawn for **safety reasons** (presence of active lesions in the oral cavity/sublingual region or suffering side effects or adverse events associated with the use of the investigational product). List of side effects and adverse reactions are listed below*

Stopping Criteria:

- 1. Participant is unwilling to continue in the study.
- 2. Lack of compliance with protocol.
- 3. Investigator or study sponsor stops the study for any reason.

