- 4. Participant is enrolled in error or lost to follow-up (lost to follow-up will be defined as a subject failing to attend planned study visits or failure to respond to contacts by study personnel after documented 2 attempts).

*Potential Side Effects and/or Adverse Events (AEs):

- 1. Feelings of anxiety (nervousness, restlessness or being tense, feelings of danger, panic, or dread), paranoia, or negative mood (depression or suicidal thoughts), or paranoia.
- 2. Suicidal ideation
- 3. Poor quality of sleep (persistent insomnia).
- 4. Feelings of extreme fatigue, sleepiness or drowsiness.
- 5. Feelings of nausea (upset stomach, vomiting or gastro-intestinal (GI) distress (e.g. diarrhea).
- 6. Change in or loss of appetite.
- 7. Feelings of light-headedness or dizziness.
- 8. Visual disturbances such as blurry/double vision.
- 9. Hypotension, hypertension, tachycardia, heart palpitations, syncope or dyspnea.
- 10. Development of a skin rash with redness and itching.

Each participant will be provided a detailed safety monitoring checklist of side effects and/or adverse reactions that they may potentially experience from ingesting the investigational product. Suicidal thoughts are not expected to be common, and there is no evidence that we know of about any association of CBD to suicide. In the unlikely event that a research participant would indicate suicidal thoughts or ideation during the visits or phone calls, they will be immediately interviewed for a formal assessment by [name] or Research Coordinator [name] (both are trained to perform such an assessment). If the assessment finds out they are not seriously suicidal, they can continue in the study. Reversely, if we the assessment finds the patient is serious about their intentions, we will either call 911 or have them agree to go to an ER for evaluation. The patient will be asked to to stop assuming CBD. In that case, we will continue to follow them if we do refer them somewhere. At the end of the study, we will try to assess whether there is any possibility that the CBD product itself is associated with the suicidal thinking or behavior.

[figure not shown]

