Screening: Study coordinator will screen candidate to determine if they meet the inclusion criteria for the study. The baseline visit activity will be described to the patient. The patient will sign the consent form. Instruction/demonstration about CBD and dropper use will be provided.

Visit 1: Baseline Evaluation before CBD administration

Activities during visit 1:

- Patient reads and signs the consent form.
- Patient completes a brief form providing information (e.g. age, address, phone number, etc., health history).
- Measure of patient's height, weight, and vital signs (HR, blood pressure, body temperature).
- Patient completes a urine drug test
- Patient completes a urine pregnancy test is they have the ability to become pregnant
- Patient fills questionnaires: PASS (Pain Anxiety Symptom Scale; four dimensions of pain measured: cognitive anxiety, escape/avoidance, fearful appraisal, physiological anxiety), VAS (Pain Experience Visual Analogue Scales; anxiety, depression, anger), PSQI (Pittsburg Sleep Quality Index; self-report used to assess a subject's usual quality of sleep)
- A trained nurse or technician draws a blood sample
- The patient is given 2 30mL bottles with a syringe dropper with instructions/demonstration to take the solution under the tongue (0.5 cc ~1/2 dropper) twice per day (BID), 12 hours apart (morning and evening), at the prescribed daily dosage (62.5mg/day).
- The patient schedules the next test visits to the laboratory.
- The patient receives \$100 for completing this visit.

Visit 2: Follow-up after a month period of CBD administration

Activities during visit 2 (day 26-34):

- Measure vital signs of the patient as in visit 1.
- Questionnaire filling as in visit 1.
- Blood draw as in visit 1.
- The patient schedules the next test visits to the laboratory.
- The patient receives \$100 for completing this visit.

Visit 3: Follow-up after a two-month period of CBD administration

Activities during visit 3 (day 56-64):

- Measure vital signs of the patient as in visit 1.
- Questionnaire filling as in visit 1.
- Blood draw as in visit 1.
- The patient schedules the next test visits to the laboratory.
- The patient receives \$100 for completing this visit.

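### Cheap safety improvement: repeat the urine pregnancy test at visit 2, since the visible schedule tests only at visit 1, when the full 60-day CBD supply is handed out

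*Combined protocol and SAP*

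**What the plan says.** - **Eligibility (section 6, Recruitment strategy).** The exclusions include "pregnancy, and current marijuana or CBD use (urine drug screen"), and lactating women are excluded as well. Among the inclusion criteria, "patients must agree to practice acceptable methods of birth control". The accepted methods range from sterilisation and long-acting devices to the pill, patch, ring and condoms. The population is 5 to 7 men and women aged 21-60.
- **Testing (section 6, Experimental Procedures).** Visit 1 lists: "Patient completes a urine pregnancy test is they have the ability to become pregnant". The next list, headed "Activities during visit 2 (day 26-34"), repeats vital signs, questionnaires and the blood draw. Visit 3 (day 56-64) does the same. Neither list has a urine test.
- **Supply (section 6, Investigational Product & Dosing Schedule).** "Each participant will be provided two 30mL bottles (2000mg CBD per bottle) with a syringe dropper during their initial (baseline) visit", to be taken as 0.5 mL twice daily. Section 5 sets dosing at 60 days.
- **Routes that could act on a known pregnancy (section 6, Safety Monitoring and Stopping Criteria).** There is a clause beginning "The PI/physician decides that the participant should be withdrawn for" safety reasons, and its examples are oral lesions and adverse events linked to the product. The stopping criteria include "Lack of compliance with protocol" and "Participant is enrolled in error or lost to follow-up". Participants also watch for checklist events themselves, and staff contact them weekly about missed doses.

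**The concern.** By excluding pregnancy and requiring birth control, the plan has already decided that pregnant women should not take the product. After visit 1, the visible text has no planned step that would find a pregnancy. Because all the product is handed over at once, no later dispensing step prompts a recheck.

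Two groups could be exposed without anyone knowing: women who conceived shortly before entry, too early for the visit 1 test to show it, and women who conceive early in dosing. Both could continue through the second month although they attend in person around day 30. What is at stake is participant safety. Section 7 states that there is no known direct benefit to participants, so nothing offsets avoidable exposure in an excluded group. No estimate, sample size or analysis depends on this point.

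**Working it through.** **Inputs from the protocol.** Two 30 mL bottles; 0.5 mL twice daily; 60 days of dosing; visit 2 at day 26-34; 5 to 7 participants.

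**Assumptions not in the protocol.** Contraceptive failure *a* = 0.5% to 15% per year; lag from conception to a positive urine test = 10 to 21 days; number of participants able to become pregnant = 0 to 7.

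**1. Does the visit 1 supply cover all dosing?** (2 × 30 mL) / (2 × 0.5 mL/day) = 60 days, which reproduces the stated 60 days. By the stated milligram doses, 4000/63 = 63.5 days and 4000/62.5 = 64.0 days. On either basis the full course is dispensed at visit 1.

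**2. Exposure spared by a stop at visit 2.** 60 − 34 = 26 days to 60 − 26 = 34 days.

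**3. Conceptions that a visit 2 test would catch.**
- During dosing, the window is the visit day minus the lag: 26 − 21 = 5 days to 34 − 10 = 24 days. As a share of 60 dosing days this is 5/60 = 8% to 24/60 = 40%.
- Before entry but missed at visit 1, the window equals the lag: 10 to 21 days.
- Together: (visit day − lag) + lag = visit day, so 26 to 34 days whatever the lag.

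**4. Chance per woman able to conceive.** Risk = 1 − (1 − a)^(d/365), with d the window in days.

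| Window | Low end | High end |
|---|---|---|
| During dosing | a = 0.005, d = 5: 0.007% | a = 0.15, d = 24: 1.06% |
| Before entry, missed at visit 1 | a = 0.005, d = 10: 0.014% | a = 0.15, d = 21: 0.93% |
| Both combined | a = 0.005, d = 26: 0.036% | a = 0.15, d = 34: 1.50% |

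The extremes of the first two rows use different lags, so they do not add to the third row; the combined row follows directly from the visit day. The calculation counts every conception in the window and removes none that would be noticed without the test. It also applies the same failure rate before entry; the pre-entry part would be larger if contraception was not in use then.

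**5. Do other visible provisions supply a later test?** None does. The visit lists are not exhaustive: the adverse-event checklist is to be read out at each laboratory visit, yet it is missing from the lists. The absence therefore had to be checked across the whole protocol. Screening names no test, pregnancy is neither a checklist event nor a stopping criterion, and the weekly contacts are described as asking about missed doses. Checklist symptoms force a stop only when judged due to the product and graded moderate to severe, so nausea or fatigue from a pregnancy would not by itself end dosing.

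**The case against.** The strongest reply is that this is a preference. Pregnancy is an entry criterion and is tested at entry; the chosen control after that is agreement to contraception. That is a coherent design, and the point is rated only as an improvement for that reason. A reader might infer that the protocol contradicts itself, but nothing visible commits it to continued testing.

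A second reply is that the benefit is easily overstated. This stands. A pregnancy missed at visit 1 would be at least 26-34 days past conception by visit 2, and up to 26 + 10 = 36 to 34 + 21 = 55 days, so some women would already know. Fatigue, nausea, appetite change and dizziness are on the checklist, and any positive answer goes to the study physician, who must consider causes other than the product. In a woman able to conceive, that is a natural moment to think of pregnancy. A reader might take 1.5% as the expected gain; it is a ceiling.

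A reader might also infer that the trial has no means of acting on a pregnancy. The text does not support that either: withdrawal for safety reasons (by extension, since its examples do not include pregnancy), non-compliance and enrolment in error could all be used once a pregnancy is reported or suspected. What they lack is detection.

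Third, not everything is visible. The safety section relies on existing monitoring guidelines that the protocol does not reproduce, and the consent pages and one figure in that section are unavailable. Any of these may already deal with pregnancy, so the finding is limited to the visible schedule.

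Finally, the remedy is partial: a visit 2 test misses 60-92% of conceptions during dosing. That limits its value, but at this cost it does not remove it.

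**Conclusion.** The point holds as an optional, low-cost safety improvement. In the visible text, pregnancy is tested at visit 1 only, while pregnancy is excluded, birth control is required and 60 days of product leave with the participant at that visit. A positive test at visit 2 would spare 26-34 of the 60 dosing days.

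The added benefit is at most about 0.04-1.5% per woman able to conceive. This rests on an assumed failure rate of 0.5-15% per year, taken to apply shortly before entry as well as during dosing. It is nil if no participant can become pregnant; the protocol gives no sex split, includes men and enrols up to age 60. The protocol gives no figure for harm from CBD in pregnancy, so the health consequence is not quantified.

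**What to change.** Make two small additions.

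1. In the visit 2 activities, repeat the visit 1 urine pregnancy test under the same condition, for participants able to become pregnant.
2. In the stopping criteria, state that CBD stops on a positive pregnancy test, pending direction from the study physician and the IRB.

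No test is proposed at visit 3, because dosing is ending by then. If the unreproduced guidelines or the consent form already provide for a later test, listing it under visit 2 is enough.

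The cost is 0 to 7 urine strips at a visit that already takes place, a little staff time and a two-line amendment. The number of participants, samples (15-21) and cells (75,000-105,000) planned does not change. Most conceptions later in dosing would still be missed.

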Primary Outcomes: This study takes a single-cell perspective, i.e., we will collect a large number of cells from a small number of patients, and we will measure RNA expression per single cell (not per patient). Note that from the single cell point of view, the number of patients (5-7) is sufficient to derive statistically viable results, as we will collect 5,000 cells from each patient at each time point (total 75,000-105,000 cells). Each cell will be sequence individually to read the RNA expression from a panel of approximately 20,000 genes. Cells will be pooled from all patients, and clustered via unsupervised algorithms into clusters of different cell types (e.g. T cells, B cells, monocytes). Our primary outcomes will be the extraction of gene expression patterns (RNA) from specific immune cell types found in PBMC (e.g., B cells, T cells, monocytes). We will regress these gene markers against the variation in baseline inflammation (C-reactive protein, erythrocyte sedimentation rate, and procalcitonin). After CBD administration to obtain CBD-related biomarkers for inflammation reduction. The difference in gene expression will be measured in fold change, p-value, and ratio of cell fraction expressing the marker gene. These biomarker gene will be unique for each cell type. We expect to extract specific biomarkers for each cell type and understand how CBD alters gene expressions of different immune cells in a different way-overall, we expect the genes of the MAPK signaling pathway (MAPK families play an important role in complex cellular programs like proliferation, differentiation, development, transformation, and apoptosis) to be strongly altered.

Secondary Outcomes. Self-report pain ratings will be used to determine peak pain intensity and pain persistence. The brief pain inventory (BPI) will be used to self-report pain perception. The inventory consists of rating pain on a visual analog scale (VAS). A 10cm line is drawn with 0 (no pain) on the left pole and 10 (worst pain imaginable) on the right pole. The inventory asks participants to rate their level of pain by placing a slash on the line that best represents their current level of pain as well as pain at its worst, best and average over the past 24 hours. The highest worst pain intensity reported during the intervention will be recorded as the peak pain intensity.

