Participants will complete self-report questionnaires to identify their level of pain-related anxiety and sleep quality during the course of the intervention. The **Pain Anxiety Symptom Scale** (PASS-20) is a 20 item, 5-point rating scale that assesses 4 theoretically distinct components of pain-related anxiety including cognitive anxiety, fear of pain, escape/avoidance behavior, and physiological anxiety [7]. The **Pittsburgh Sleep Quality Index** (PSQI) is a self-report questionnaire that assesses sleep quality over a 1-month time interval. The measure consists of 19 individual items, creating 7 components that

produce one global score, and takes 5–10 minutes to complete.[8] The SF-12 is one of three generic measures (along with the SF-20 and SF-36) from the Medical Outcomes Study (MOS). It consists of 12 items in 8 domains: physical functioning, role-physical, role-emotional, bodily pain, general health, vitality, social functioning and mental health, allowing for the generation of physical and mental health summary scores. During the visits, we will also administer a standard demographic questionnaire.

A **Data and Safety Monitoring Plan** will consist of two components: (1) overseeing participant safety and data monitoring, and (2) performance of monitoring. Since this project is viewed as low potential risk, all key personnel will perform all data and safety monitoring on an as needed basis. The principal investigator will meet quarterly with all members of the research team to discuss data and safety monitoring issues and any issues that arise will be handled in a manner that is consistent with the University of Florida's policies. Annually, data and safety monitoring information will be reported to and reviewed by the University of Florida IRB.

7. Possible Benefits

There is no known direct benefit from participating in this study. All study participants will be paid for their time performing research related duties that may or may not be considered a benefit. In this study, participants will receive \$300 for completion of 3 inperson sessions. There are no other obvious benefits to the study participant.

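### The visit questionnaire list does not name the SF-12, and covers the BPI only if the listed VAS was meant to be it; the visit schedule and Secondary Outcomes need reconciling

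*Combined protocol and SAP*

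**What the plan says.** In section 6 (Research Plan), Experimental Procedures, the block titled "Visit 1: Baseline Evaluation before CBD administration" has one questionnaire bullet. It opens "Patient fills questionnaires: PASS (Pain Anxiety Symptom Scale; four dimensions of pain measured", goes on to "VAS (Pain Experience Visual Analogue Scales; anxiety, depression, anger", and closes with the PSQI. Visits 2 and 3 each say only "Questionnaire filling as in visit 1".

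The Secondary Outcomes text in the same section sets out a different group of forms. On pain it says "The brief pain inventory (BPI) will be used to self-report pain perception", and then "The inventory consists of rating pain on a visual analog scale (VAS". The ratings asked for are "current level of pain as well as pain at its worst, best and average over the past 24 hours", and the highest worst-pain rating during the intervention becomes the peak pain intensity. It then describes the PASS-20 and the PSQI. Finally it introduces a general health measure: "The SF-12 is one of three generic measures (along with the SF-20 and SF-36) from the Medical Outcomes Study (MOS". No visit is given there for the BPI or the SF-12.

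Section 5 (Specific Aims) lists pain relief among the secondary outcomes. Specific Aim 1 is to compare quality-of-life measures, including pain and pain-related symptoms where present.

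**The concern.** Site staff work from the visit list. It has no wording such as for example or including, so it reads as complete for questionnaires. It names neither the SF-12 nor the BPI.

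Two things are at stake. The SF-12 is the only general quality-of-life instrument in the document, and quality of life is the subject of Aim 1. The BPI is the only described form that rates pain intensity, and pain relief is a named secondary outcome that also enters the Aim 2 hypothesis.

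Timing makes the gap hard to repair. Visit 1 is the only visit before CBD starts. If a form is added after a patient has begun treatment, that patient has no before value. With 5 to 7 patients, each lost baseline removes between one-seventh and one-fifth of a before-after comparison.

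**Working it through.** No power or error-rate figure bears on this point. The check sets the two sections side by side.

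*Inputs.* Visit 1 list and its repetition at Visits 2 and 3: Experimental Procedures. Instruments and their content: Secondary Outcomes. Patients (5 to 7) and time points (3): Sample collection and processing.

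*Step 1: planned completions per form.* 5 × 3 = 15 and 7 × 3 = 21. This agrees with the plan's own count of 15 to 21 samples. Pre-CBD values per form: 5 to 7.

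*Step 2: instruments against visits, reading the list literally.*

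| Instrument | Described under Secondary Outcomes | Visits at which it is named | Completions that follow |
|---|---|---|---|
| PASS | yes | 3 of 3 | 15 to 21 |
| PSQI | yes | 3 of 3 | 15 to 21 |
| SF-12 | yes | 0 of 3 | 0 |
| BPI | yes | 0 of 3 by name; 3 of 3 if the listed VAS is the BPI | 0, or 15 to 21 |
| VAS for anxiety, depression, anger | not in that form | 3 of 3 | 15 to 21 |

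Of the four described questionnaires, one (SF-12) is unnamed on either reading of the VAS. Two (SF-12 and BPI) are unnamed if the VAS is a separate form.

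*Step 3: could the listed VAS be the BPI?* In favour: the BPI is said to use a visual analogue scale, and the listed scale has pain experience in its title. Against: the BPI ratings are current, worst, best and average pain, while the listed domains are anxiety, depression and anger. The overlap is 0 of 4. Depression and anger are not outcomes in the Secondary Outcomes text. The natural reading is two different forms, but the document does not settle it.

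*Step 4: is the timing given elsewhere?* The adverse-event checklist is also missing from the visit lists, but Safety Monitoring and Stopping Criteria separately requires it at each laboratory visit. No comparable sentence fixes visits for the SF-12 or the BPI.

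**The case against.** The strongest reply is that the visit lists are abbreviated. They leave out the adverse-event checklist and the brief baseline physical examination, both required elsewhere, and nobody would conclude that those will not be done. The Secondary Outcomes text says the BPI will be used. After describing the forms, it adds that a demographic questionnaire will also be administered during the visits, which implies that the others are given then too. This stands. A reader might infer from the zero counts that the SF-12 is certain to go uncollected, or that Aim 1 fails. The document does not support either inference: the counts show what the list names, not what staff will do.

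The likely harm also has limits:

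- Aim 1 names no instrument, and PASS and PSQI are scheduled at every visit, so at most its general quality-of-life part is exposed.
- No sentence says outright that participants will complete the SF-12. It may be leftover text.
- Chronic pain is not required for enrolment, so pain relief may not be assessable in some patients whichever form is used.
- Peak pain intensity, as defined, covers the intervention period and needs no pre-CBD value. The lost-baseline argument applies to change in pain and in SF-12 scores, not to peak pain. Peak pain would still need the worst-pain rating at the later visits.

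None of this removes the mismatch. A reader of the document still cannot tell at which visits the SF-12 or the BPI is to be completed.

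**Conclusion.** The concern holds as an inconsistency between the outcome section and the visit schedule. The SF-12 is named at none of the 3 visits. The BPI is named at none unless the listed VAS was intended to be it, and its stated domains do not fit that reading.

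The consequences are conditional on staff following the list literally. Then there would be no SF-12 among 15 to 21 planned completions, including none of the 5 to 7 pre-CBD values. If the VAS is not the BPI, the same would be true of the pain-intensity ratings.

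Severity is minor to moderate. Only secondary outcomes are touched; the gene-expression primary outcome and the PASS and PSQI comparisons are not. It is worth settling before enrolment because a missed baseline cannot be collected later.

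**What to change.** Before the first patient is enrolled:

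1. Add the SF-12 by name to the Visit 1 questionnaire bullet. Visits 2 and 3 then inherit it. If the SF-12 is not intended, remove it from the Secondary Outcomes text and state which listed measure serves quality of life in Aim 1.
2. Add the four BPI pain ratings to the same bullet and keep the listed anxiety, depression and anger scale beside them. Replace that scale's stated domains only if the sponsor confirms it was meant to be the BPI. Doing so would drop three ratings now scheduled at every visit, and that loss should be acknowledged.

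The cost is wording plus at most 12 + 4 = 16 short self-report items at each of three existing visits, or 48 per patient. No visit is added. The document gives no completion time for either form, so the added minutes cannot be stated.
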